#### **4.5.1.10 Safety Surveillance for Squamous Cell Carcinoma**

A thorough head and neck examination to monitor for non-cutaneous SCC, consisting of at least a visual inspection of the oral mucosa and lymph node palpation, must be performed by the treating physician or other qualified physician at screening for all patients enrolled. The most current examination from the antecedent protocol may be utilized as the screening examination for the extension (rollover) protocol if it was conducted within 30 days prior to first dose of vemurafenib on Study GO28399.

Thereafter, the head and neck examination will be repeated by the treating physician or other qualified physician every other treatment cycle ( $\pm 21$  days) after initiation of study treatment and every other cycle through Cycle 15. Then, for patients still receiving treatment, the head and neck examination will continue to be conducted every third cycle starting at Cycle 18, (i.e., screening and every three cycles per the Cycle 18+ period in the Schedule of Assessments [[Appendix 1](#)] for patients with  $\geq 17$  cycles of vemurafenib on an antecedent study), or until withdrawal of consent, death, or loss to follow-up (whichever occurs earliest).

Chest CT scans must be performed at baseline, within 30 days before the start of study treatment on Study GO28399, and then every 6 months (with a window of  $\pm 21$  days) after the initiation of treatment until death, withdrawal of consent, *or* loss to follow-up, whichever occurs first. Available routine chest CT scans from the antecedent study or those performed for tumor assessments during the study period (at the discretion of the investigator, per local institutional standard of care) that fit the required timeline specification can be used for this safety surveillance.

Additionally, all patients are required to undergo examination of the anus by the treating physician or his/her designee at baseline and at the end of treatment visit. The most current examination may be utilized as the baseline examination for the extension (rollover) protocol if it was conducted during the screening period or conduct of the antecedent protocol.

Female patients must have a pelvic examination (including evaluation of the uterine cervix and Papanicolaou [Pap] smear) at baseline and at the end of treatment visit performed by gynecologist or designee. The most current examination may be utilized as the screening examination for the extension (rollover) protocol if it was conducted during the screening period or the conduct of the antecedent protocol.

#### **4.5.1.11 Exploratory Molecular Assessments**

- Patient specimens for dynamic (non-inherited) biomarker discovery and validation should be collected from patients participating in this study if the sample is available by routine biopsy.

- Analyses will depend on the type of lesion and may include but are not limited to:
  - BRAF and H/K/N-RAS mutation analysis
  - HPV diagnosis (HPV genotype, p16 expression)
  - Epidermal growth factor receptor (EGFR) expression/gene copy number

At least 6–10 formalin-fixed paraffin embedded tissue slides are required.

## **4.5.2 Timing of Study Assessments**

### **4.5.2.1 Screening/Baseline and Pretreatment Assessments**

Written informed consent for participation in the study must be obtained before performing any study-specific baseline tests or evaluations. Informed Consent Forms for enrolled patients and for patients who are not subsequently enrolled will be maintained at the study site.

The investigator must maintain a patient Enrollment and Identification Code List.

Results from the study completion visit or other prior visit assessment in the antecedent protocol may be used as screening/baseline for this extension (rollover) study, if within time intervals, as specified in this section and [Appendix 1](#); screening/baseline is combined into one visit.

Under no circumstance will patients be permitted to re-enroll in the study if they have previously enrolled in this study and completed/discontinued treatment as specified.

All required screening/baseline procedures including data collection or transfer from the antecedent study must be performed after the patient has provided informed consent within a maximum window of 15 days from the last *dose of study drug* in the antecedent study to until the *first dose* of treatment in this extension (rollover) study, or as specified in Section [4.5.1](#) and [Appendix 1](#) for specific assessments.

All patients will be closely monitored for safety and tolerability during all cycles of therapy and at the study completion visit. After signing the Informed Consent Form, all adverse events and serious adverse events (including serious adverse events due to invasive procedures required for the study such as biopsies) will be collected. Patients will be assessed for adverse events prior to each subsequent cycle and as necessary throughout the study. All adverse events will be recorded until 28 days after the last dose of study treatment or until initiation of another anti-cancer therapy, whichever occurs first.

Visits are based on a 28-day cycle. If the timing of a protocol-mandated procedure coincides with a holiday or another scheduling conflict that precludes the visit, the visit should be scheduled within  $\pm 3$  days of the date in question, which may be earlier or later.

## Screening/Baseline Assessments:

Screening/baseline is combined into one visit.

All screening/baseline assessments are outlined in the Schedule of Assessments ([Appendix 1](#)). Note that *for all screening/baseline assessments*, results of study assessments in the antecedent protocol may be utilized as the baseline assessments for the current protocol at the permitted intervals as noted below.

- Review of eligibility criteria
- Significant medical history—from the antecedent study
- Vital signs (blood pressure, pulse, respiratory rate, temperature)
- Height and weight (part of the physical examination)
- ECOG Performance Status
- Physical examination: An examination from the antecedent protocol may be utilized as the screening examination for the extension (rollover) protocol if it was conducted within 30 days prior to first dose of vemurafenib on Study GO28399.
- Anus, anal canal, and pelvic examination (if female): A prior examination may be utilized as the screening examination for the extension (rollover) protocol if it was conducted during the screening period or the conduct of the antecedent protocol.
- Hematology (WBC count, hemoglobin, hematocrit, platelet count, WBC differential count [neutrophils, bands, lymphocytes, eosinophils, basophils, and monocytes]). An examination from the antecedent protocol may be utilized as the screening examination for the extension (rollover) protocol if it was conducted within 15 days prior to first dose of vemurafenib on Study GO28399.
- Serum chemistries (sodium, potassium, chloride, bicarbonate, BUN, creatinine, calcium, phosphate, magnesium, total and direct bilirubin, albumin, AST, ALT, LDH, and ALP). An examination from the antecedent protocol may be utilized as the screening examination for the extension (rollover) protocol if it was conducted within 15 days prior to first dose of vemurafenib on Study GO28399.
- Serum pregnancy test (for women of childbearing potential, including premenopausal women who have had a tubal ligation) within 7 days preceding the planned first dose of treatment on Study GO28399.
- 12-lead ECG recording, according local institutional standards. An examination from the antecedent protocol may be utilized as the screening examination for the extension (rollover) protocol if it was conducted within 14 days prior to first dose of vemurafenib on Study GO28399.
- Adverse events (from last treatment on the antecedent protocol)
- Concomitant medications and treatments

The following procedures must be performed in the current protocol only after patient eligibility has been confirmed and informed consent has been obtained:

- Thorough head and neck evaluation (completed by treating physician). An examination from the antecedent protocol may be utilized as the screening examination for the extension (rollover) protocol if it was conducted within 30 days prior to first dose of vemurafenib on Study GO28399.
- CT scan of chest (for SCC risk management; can use routinely scheduled radiologic assessment for tumor burden while patient is in the study). An examination from the antecedent protocol may be utilized as the screening examination for the extension (rollover) protocol if it was conducted within 30 days prior to first dose of vemurafenib on Study GO28399.
- Dermatology evaluation (required for all patients prior to Cycle 1, Day 1 in the extension [rollover] protocol). An examination from the antecedent protocol may be utilized as the screening examination for the extension (rollover) protocol if it was conducted within 30 days prior to first dose of vemurafenib on Study GO28399.
- Any evaluable and measurable disease will have been documented as specified for screening in the antecedent protocol and/or according to local institutional standards of care. Type and pathologic stage of current underlying cancer will be assessed according to the American Joint Committee on Cancer v7.0 classification (Edge SB et al. 2010). This assessment will be performed with the use of physical examination and imaging studies (such as contrast-enhanced CT or MRI of the C/A/P and contrast-enhanced MRI of the brain [or CT if MRI is not generally available]), according to local institutional standard of care. A prior examination may be utilized as the baseline/screening examination for the extension (rollover) protocol if it was conducted during the screening period or the conduct of the antecedent protocol.

See [Appendix 1](#) for the Schedule of Assessments.

#### **4.5.2.2 Assessments during Treatment**

Except where specified, all assessments will be performed on the day of the specified visit  $\pm 3$  days for assessments scheduled every 28 days, unless otherwise specified in the protocol and the Schedule of Assessments (see [Appendix 1](#)). Assessments scheduled on a day of study drug administration should be performed prior to study drug administration unless otherwise noted.

- Imaging for tumor assessments during the study period will be performed at the discretion of the investigator per local institutional standard of care for the purpose of defining progression of disease.

*The following assessments may be performed  $\leq 4$  days prior to the scheduled clinic visit (as applicable) for Day 1 of each treatment cycle:*

- *Hematology*

- *Serum chemistries*
- ECG

Results of the assessments must be reviewed by the investigator prior to any study drug administration on the first day of treatment of a given cycle.

See [Appendix 1](#) for the Schedule of Assessments performed during the treatment period.

Additional physical examination, clinical, laboratory (e.g., hematology, chemistry, ECG, etc.) and other diagnostic studies may be conducted at scheduled and non-scheduled timepoints to evaluate safety and to assess tumor status, as may be clinically indicated, at the discretion of the investigator or per institutional guidelines.

Patients who have received a minimum of 17 cycles of vemurafenib treatment in the antecedent study will undergo a screening/baseline visit and then proceed to every third-cycle study visits commencing with the Cycle 18 visit.

#### **4.5.2.3 Assessments at Unplanned Visits**

Additional physical examination, clinical, laboratory (e.g., hematology, chemistry), and other diagnostic studies may be conducted at scheduled and non-scheduled timepoints to evaluate safety and to assess tumor status, as may be clinically indicated, at the discretion of the investigator or per institutional guidelines.

#### **4.5.2.4 End of Treatment Visit**

Patients who complete the study or discontinue from the study drug for any reason will be asked to return to the clinic within 28 days after their last dose of vemurafenib or before starting new non-protocol therapy (whichever is earliest) for an end of treatment visit. The visit at which a response assessment showed disease progression will be used as the end of treatment visit. The following assessments will be performed:

- Physical examination (including examination of the eyes, ears, nose, and cardiovascular, dermatological, musculoskeletal, respiratory, gastrointestinal, genitourinary, and neurological systems and the safety surveillance assessment for new primary malignancy including head and neck, anus, and pelvic [for female patients only] examinations)
- Vital signs
- 12-lead ECG (prior to blood samples)
- ECOG Performance Status
- Hematology
- Serum chemistries
- Concomitant medications
- Adverse events

Refer to [Appendix 1](#) for assessments to be performed at the study completion or early termination visit.

#### **4.5.2.5 Adverse Event Follow-Up**

After the study completion visit, ongoing adverse events thought to be related to study treatment will be followed until the event has resolved to baseline grade, is assessed by the investigator as stable, new anti-tumor treatment is initiated, the patient is lost to follow-up, the patient withdraws consent, or it has been determined that study treatment or participation is not the cause of the adverse events.

After the study completion visit, investigators should report only serious adverse events that are deemed related to study treatment.

After the study completion/early termination visit, adverse events should be followed as outlined in Sections [5.5](#) and [5.6](#).

See [Appendix 1](#) for the schedule of follow-up assessments.

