#### **4.5.1.6 Clinical Safety Assessments**

NCI CTCAE v4.0 will be used to characterize the toxicity profile of the study treatment. All patients will be assessed for adverse events. After signing the Informed Consent Form, all adverse events and serious adverse events (including serious adverse events due to invasive procedures required for the study, such as biopsies) will be collected. Patients will be assessed for adverse events at each study visit. All adverse events will be recorded until 28 days after the last dose of study treatment or until initiation of another anti-cancer therapy, whichever occurs first.

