#### **4.5.3 Patient Discontinuation**

The investigator has the right to discontinue a patient from study drug or withdraw a patient from the study at any time. In addition, patients have the right to voluntarily discontinue study drug or withdraw from the study at any time for any reason. Reasons for discontinuation of study drug or withdrawal from the study may include but are not limited to the following:

- Patient withdrawal of consent at any time
- Any medical condition that the investigator or Sponsor determines may jeopardize the patient's safety if he or she continues in the study
- Investigator or Sponsor determines it is in the best interest of the patient.
- Patient non-compliance, specifically defined as patient's refusal to take the required doses of study drugs, unless for a reason, as defined below

In cases where the patient decides to prematurely discontinue study treatment ("refuses treatment"), he or she should be asked if he or she can still be contacted for further information. The outcome of that discussion should be documented in both the medical records and in the eCRF. If the patient is lost to follow-up, the investigator should contact the patient or a responsible relative by telephone followed by registered mail to establish the reason for the withdrawal as completely as possible. A complete final evaluation at the time of the patient's withdrawal should be made with an explanation of why the patient is withdrawing from the study.

When applicable, patients should be informed of circumstances under which their participation may be terminated by the investigator without the patient's consent. The investigator may withdraw patients from the study in the event of intercurrent illness,

adverse events, treatment failure after a prescribed procedure, lack of compliance with the study and/or study procedures (e.g., dosing instructions, study visits), cure, or any reason where it is believed by the investigator that it is in the best interest of the patient to be terminated from the study. Any administrative or other reasons for withdrawal must be documented and explained to the patient. Any patient who discontinues will be encouraged to return to the study center for a study completion visit.

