#### **4.5.3.1 Discontinuation from Study Drug**

Patients may continue to receive treatment with vemurafenib until disease progression (as defined by the investigator, according local institutional standard of care), unacceptable toxicity, or any other discontinuation criterion is met, as follows, whichever occurs first.

- Disease progression as assessed per institutional standards of care
  - Progressive disease during the antecedent protocol. If approval to treat beyond progression was already given in the antecedent protocol, the patient may roll over into the current protocol.
  - Under special circumstances, when it is believed that the patient may clinically benefit from continued therapy with vemurafenib (e.g., in case of mixed progression or progression of single lesion or appearance of a new single lesion), enrollment into this protocol and dosing beyond progression may be considered if it is judged by the investigator, in consultation with the Sponsor, to be in the best interest of the patient. All such cases will require approval of the Sponsor before continuing study drug treatment within this protocol.
- Intolerance of vemurafenib
- If treatment is suspended more than 28 days, the patient should be withdrawn from the study
- Initiation of other cancer medication
- Pregnancy

Patients who discontinue study drug prematurely will be asked to return to the clinic for an end of treatment visit (see Section 4.5.2.4 and Appendix 1). The primary reason for premature study drug discontinuation should be documented on the appropriate eCRF. Patients who discontinue study drug prematurely will not be replaced.

*All patients who discontinue vemurafenib treatment will be followed for safety surveillance per the investigator's discretion.*

Note: New primary melanomas identified as part of the dermatologic risk management plan outlined in Section 4.5.1.9, which are completely excised and without need for additional therapy, do not require patient discontinuation from study treatment.

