### **5.3.1 Adverse Event Reporting Period**

Investigators will seek information on adverse events at each patient contact. All adverse events, whether reported by the patient or noted by study personnel, will be recorded in the patient's medical record and on the Adverse Event eCRF.

After informed consent has been obtained but prior to initiation of study drug, only serious adverse events caused by a protocol-mandated intervention should be reported (e.g., serious adverse events related to invasive procedures such as biopsies).

After initiation of study drug, all adverse events, regardless of relationship to study drug, will be reported until 28 days after the last dose of study treatment or until initiation of another anti-cancer therapy, whichever comes first.

*Instructions for reporting adverse events that occur after the adverse event reporting period are provided in Section 5.6.*

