### **5.6 ADVERSE EVENTS THAT OCCUR AFTER THE ADVERSE EVENT REPORTING PERIOD**

*The Sponsor should be notified if the investigator becomes aware of any serious adverse event that occurs after the end of the adverse event reporting period (defined as 28 days [see Section 5.3.1] after the final dose of study drug), if the event is believed to be related to prior study drug treatment. These events should be reported through use of the Adverse Event eCRF. However, if the EDC system is not available, the investigator should report these events directly to the Sponsor or its designee, either by faxing or by*

*scanning and emailing the paper Clinical Trial Serious Adverse Event/Adverse Event of Special Interest Reporting Form using the fax number or email address provided to investigators.*

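### Section 4.5.2.5 restricts reporting to related serious adverse events from the closing visit, which can precede day 28, and so conflicts with the all-adverse-event window that runs to day 28

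*Combined protocol and SAP*

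**What the plan says.** The protocol gives the boundary for adverse event (AE) reporting in several places.

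- **Section 4.5.2.5 (Adverse Event Follow-Up):** "After the study completion visit, investigators should report only serious adverse events that are deemed related to study treatment". The next sentence sends the reader to Sections 5.5 and 5.6 for follow-up of events after that visit.
- **Section 4.5.1.6:** "All adverse events will be recorded until 28 days after the last dose of study treatment or until initiation of another anti-cancer therapy", whichever is first. Section 4.5.2.1 repeats this rule.
- **Section 5.3.1 (Adverse Event Reporting Period):** "After initiation of study drug, all adverse events, regardless of relationship to study drug, will be reported until 28 days after the last dose", with the same earlier stop at another anti-cancer therapy.
- **Section 5.6:** the Sponsor is to be told of "any serious adverse event that occurs after the end of the adverse event reporting period (defined as 28 days" after the final dose) if it is believed related to prior study drug.

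Four places bear on which visit Section 4.5.2.5 means.

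- Section 4.5.2.4, headed End of Treatment Visit, ends by referring to Appendix 1 "for assessments to be performed at the study completion or early termination visit".
- Section 4.5.3: "Any patient who discontinues will be encouraged to return to the study center for a study completion visit".
- Section 4.5.3.1: "Patients who discontinue study drug prematurely will be asked to return to the clinic for an end of treatment visit".
- Appendix 1 has one post-treatment column, the end of treatment visit, to be held no later than 28 days after the last dose.

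Section 4.5.2.4 also makes the visit at which progression was shown serve as the end of treatment visit.

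**The concern.** Section 4.5.2.5 switches the reporting rule at a visit. The other sections switch it at a fixed time after the last dose. The two agree only when the visit falls at the end of the window, and the protocol allows it to fall earlier.

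AEs and serious adverse events (SAEs) are the study's only outcome measures (Sections 3.5.1 and 3.5.2), and describing safety is its secondary objective (Section 2.2). A site that follows Section 4.5.2.5 literally could omit events that a site following Section 5.3.1 would report. The AE incidence planned in Section 6.3 would then mix two reporting windows without any way to see it in the tables.

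**Working it through.** The plan has no sample size calculation, power or event count, so there is no stated figure to reproduce. The check compares the texts and then counts days.

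**Step 1: identify the visit.** The term in Section 4.5.2.5 is undefined. Section 4.5.2.4 uses it for its own Appendix 1 visit. Sections 4.5.3 and 4.5.3.1 call a discontinuing patient back under the two different names. Appendix 1 has no later visit to which the term could apply. The natural reading is that the study completion visit is the end of treatment visit.

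**Step 2: find when it can occur.** Section 4.5.2.4 allows any day up to 28 after the last dose, and requires it before new non-protocol therapy if that comes first. If drug stops at the progression visit, that visit is the closing visit and d is at or near 0. Progression is the first discontinuation criterion listed in Section 4.5.3.1, so early closing visits are an expected route.

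**Step 3: compare the rules between the visit and day 28, with no new therapy started.**

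| Section | Rule in that interval | Boundary |
|---|---|---|
| 4.5.2.5 | Related SAEs only | Closing visit |
| 4.5.1.6, 4.5.2.1 | All AEs recorded | Day 28 or new therapy |
| 5.3.1 | All AEs reported, related or not | Day 28 or new therapy |
| 5.6 | Related-SAE-only rule not yet started | End of the Section 5.3.1 period |

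No text gives one of these sections precedence.

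**Step 4: count the days in conflict.** Let d be the day of the closing visit after the last dose, 0 ≤ d ≤ 28. Without new anti-cancer therapy the length is 28 - d.

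| d | 28 - d |
|---|---|
| 0 | 28 |
| 7 | 21 |
| 14 | 14 |
| 21 | 7 |
| 28 | 0 |

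If new therapy starts on day t < 28, the all-AE window closes at t and the length is t - d. For example, d = 7 and t = 14 gives 14 - 7 = 7 days.

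**Step 5: find which events have no other reporting route.** Section 5.4 requires SAEs and non-serious AEs of special interest to be reported regardless of relationship. Appendix 5 requires SAEs, related or not, through the protocol-defined follow-up period where that is longer than 15 days. Section 5.1.2.3 requires new primary invasive malignancies up to 28 days after treatment as SAEs, related or not. For these the instructions conflict but a reporting duty exists. For non-serious events not of special interest, the only competing instruction is the general all-AE window itself.

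**Step 6: check the correction.** If Section 4.5.2.5 switched at the end of the Section 5.3.1 period, the interval in Step 4 would be 0 days for every patient.

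**The case against.** The strongest reply is that the governing rule is clear elsewhere. Section 5.3.1 is the section that defines the reporting period, Sections 4.5.1.6, 4.5.2.1 and 5.1.2.2 use the same boundary, and Section 4.5.2.5 itself points to Section 5.6, which relies on it. This stands as evidence of intent: day 28 is what the authors meant. It does not remove the word 'only' from the sentence just before the pointer.

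A second reply is that Section 4.5.2.5 limits what is reported, while Sections 4.5.1.6 and 4.5.2.1 govern what is recorded. This has partial force for those two sections. It fails for Section 5.3.1, which uses the reporting verb for all AEs, so the conflict there is direct.

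A third reply is that little depends on it. The study is single-arm and descriptive, has no formal hypothesis test (Section 6), and exists mainly to provide continued access (Section 2.1). That stands, and it limits the consequence to completeness of the safety summary.

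Two stronger readings are tempting, and the documents do not support them.

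- A reader might infer that unrelated SAEs or new malignancies would go unreported. Step 5 shows that separate duties cover them.
- A reader might infer that clinic visits stop at progression while dosing continues, because the every-third-cycle clause (synopsis, Section 3.1.1, Appendix 1 notes) names progression as an end point. That clause is limited at its start to patients still on treatment. Section 4.5.2.1 says "All patients will be closely monitored for safety and tolerability during all cycles of therapy", and Section 5.1.2.2 also requires monitoring through treatment. Appendix 1 ties drug dispensing to visits, and Section 4.5.2.2 requires results to be reviewed before dosing at the start of a cycle. Likewise, the progression-visit sentence in Section 4.5.2.4 can be read as covering only patients who stop drug.

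**Conclusion.** The sentence in Section 4.5.2.5 is wrong as written and should be corrected. It conflicts directly with Sections 5.3.1 and 5.6, and with Sections 4.5.1.6 and 4.5.2.1 so far as reporting and recording are the same act. The conflict lasts up to 28 - d days per patient, from 0 to 28.

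This rests on one reading, that the study completion visit is the end of treatment visit. The text supports that reading strongly but does not state it.

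The exposure is confined to non-serious events not of special interest that arise between an early closing visit and day 28. The number of such events cannot be estimated: the documents give no distribution of closing-visit days and no post-dose event rate. A reader might try to size it from the elimination half-life in Section 1.2.1.3, but drug level measures neither missed events nor bias. No inference is affected, because none is planned.

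**What to change.** In the reporting sentence of Section 4.5.2.5, replace 'After the study completion visit' with 'After the adverse event reporting period defined in Section 5.3.1'. The section then agrees with Section 5.6, and the conflict falls to zero days for every patient.

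The cost is one phrase, with no added visit, test or patient burden. The change would go through the amendment process in Section 9.5, so it is best carried with the next amendment.

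Two clarifications are optional and are not corrections. The visit clause in the synopsis, Section 3.1.1 and the Appendix 1 notes could run to permanent discontinuation of study drug. Section 4.5.2.4 could say that the progression visit serves as the end of treatment visit only for patients who stop drug at that visit.
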